7.0 Treatment Dose Modifications

Treatment dose may be modified or held by the primary treating oncologist at their discretion. Treatment may be held a total of 4 weeks to account for toxicity. We recommend the following dose modifications in the event of \geq Grade 2 toxicity. If treatment has been held for greater than 4 weeks the patient will be discontinued from study. If dose modifications require more than 2 dose level reductions, the patient will be discontinued from the study.

Patients with grade 2 or greater neuropathy attributed to Oxaliplatin can discontinue oxaliplatin provided that they have received at least 6 cycles and be treated with single agent 5-Fluorouracil.

Growth factor support, such as pegfilgrastim, may be used at provider discretion.

Table 5. Dose Modifications Guide

Treatment	Dose Level 0	Dose Level -1	Dose Level -2
Oxaliplatin	85 mg/m ²	65 mg/m ²	50 mg/m ²
Leucovorin	400 mg/m ²	320 mg/m ²	260 mg/m ²
5-Fluorouracil (bolus)	400 mg/m ²	320 mg/m ²	260 mg/m ²
5-Fluorouracil (infusion)	2400 mg/m ²	1920 mg/m ²	1540 mg/m ²

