5.6 Discontinuation of Study

Participants may be discontinued from treatment for any of the following reasons:

1. The participant wishes to no longer participate in treatment
2. The provider in charge of the patient’s treatment withdraws the participant

3. The participant is determined to have unacceptable or intolerable toxicity
4. A participant becomes pregnant
5. A participant is diagnosed with another malignancy requiring treatment
6. The participant is lost to follow up
7. If treatment is held for greater than 28 days

All participants who are discharged from treatment and the study will continue to be followed for severe adverse events, disease free and overall survival whenever possible.

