10.0 Objectives and Data Analysis

10.1 Primary Endpoint

The primary outcome will be the rate of a complete clinical response. Response rates will be determined by the following:

- **A complete response** will consist of a digital rectal exam with normal appearing mucosa and sigmoidoscopy/proctoscopy with scarring but no nodularity or ulcerations.
- **A near complete response** will consist of digital rectal exam with smooth or minor mucosal abnormalities, and sigmoidoscopy/proctoscopy with small mucosal abnormalities, or superficial ulceration or erythematous scarring. No palpable lymph nodes but some induration/mucosal abnormalities
- **Partial response**, in our study, will be those tumors read with a $\geq 20\%$ decrease in size without obtaining near or complete response, or remaining palpable lymph nodes with partial response

- **Stable disease**, in our study, will be those tumors read with a <20% decrease in size without obtaining near or complete response, or palpable lymph nodes, no change in size on proctoscopy/sigmoidoscopy
- **Progressive disease** will be those tumors with >20% increase in size, new lesions or palpable lymph nodes.

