10.3 Data Analysis

We aim to accrue 40 participants over approximately a 5-year period. Though we hypothesize that this study will be of clinical benefit to those who may avoid surgical intervention, we have no knowledge that a similar study has been conducted. Thus, we aim to gain a preliminary estimate of the rate of locally advanced rectal cancer patients that can be spared surgical intervention through the use of neoadjuvant chemotherapy plus short course radiation. We anticipate a 30% rate of complete or near complete clinical response to neoadjuvant chemotherapy plus short course radiation at the post-radiation assessment. This rate will include subjects discontinuing mFOLFOX due to stable or progressive disease at the interval assessment or re-staging assessment in the denominator.

With an anticipated response rate of 30%, a sample size of 40 subjects produces a one-sided 95% lower-limit exact binomial confidence interval with a width of 13.4% (lower limit of 16.6%). The maximum width of a one-sided 95% lower-limit confidence interval with 40 subjects would be 16.1% when the response rate is 50%. We target the lower limit of the confidence interval to determine if this regimen demonstrates sufficient evidence of efficacy to be considered worthy of future study.

The complete or near complete response rate and associated 95% one-sided exact binomial confidence interval will be presented. Disease-free and overall survival will be described using the Kaplan-Meier method. Types and grades of adverse events will be tabulated. Changes in QOL (from baseline) will be described using means and standard deviations at each time point assessed. We will calculate these summary measures separately in those who obtain a complete or near complete response to up to 12 cycles of mFOLFOX and short course radiation and are entering watch and wait surveillance, and those who required surgery with or without radiation therapy prior to completion of mFOLFOX therapy. QOL will be measured using validated

QOL forms EORTC QLQ-30, and EORTC QLQ-CR29 as mentioned in Section 5.2, with paper-based surveys and scored according to the EORTC scoring manual [10].

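### Section 7.0 takes patients off study after a hold of more than 4 weeks or more than 2 dose-level reductions, which leaves a responder without a scheduled post-radiation assessment; section 5.6 only permits stopping treatment at the same 28-day hold

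*Combined protocol and SAP*

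**What the plan says.** Section 7.0 first gives an allowance: "Treatment may be held a total of 4 weeks to account for toxicity". It then gives two mandatory removals: "If treatment has been held for greater than 4 weeks the patient will be discontinued from study" and "If dose modifications require more than 2 dose level reductions, the patient will be discontinued from the study".

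Section 5.6 opens its list with "Participants may be discontinued from treatment for any of the following reasons", and item 7 of that list is "If treatment is held for greater than 28 days". Its closing sentence says that participants discharged from both treatment and study "will continue to be followed for severe adverse events, disease free and overall survival whenever possible".

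Section 10.3 fixes when the primary endpoint is read: "We anticipate a 30% rate of complete or near complete clinical response to neoadjuvant chemotherapy plus short course radiation at the post-radiation assessment". Section 10.1 defines a complete response by examination; it "will consist of a digital rectal exam with normal appearing mucosa and sigmoidoscopy/proctoscopy with scarring but no nodularity or ulcerations". The 10.3 denominator sentence names only patients who stop mFOLFOX for stable or progressive disease. The text under the schema (Figure 1) puts all patients into the response evaluation and gives N=30, whereas 10.3 gives 40.

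**The concern.** Sections 7.0 and 5.6 attach different consequences to the same length of hold. One is mandatory and ends study participation. The other is permissive and ends treatment. A site cannot tell from the text which to apply.

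The difference matters because the primary endpoint comes late. Section 3.0 gives patients in partial, near complete or complete response at the interval assessment a further 4 to 6 cycles, then restaging, then radiation, then a repeat assessment. A patient responding well after cycle 6 can reach a long hold or a third dose reduction in the later cycles. If 7.0 is followed, that patient leaves the study before the visit at which response is recorded. The primary result could then lose a response because of an administrative rule, not because the tumor failed to respond. In a trial of 30 or 40 patients, where 10.3 uses the lower confidence limit to judge whether the regimen merits further study, each such loss is visible.

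**Working it through.** **1. The two rules side by side.**

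| | 7.0 | 5.6 |
|---|---|---|
| Hold limit | more than 4 weeks | more than 28 days (4 × 7 = 28, the same limit) |
| Force | will | may |
| Ends | study | treatment (but the section heading refers to the study, and the closing sentence to both) |
| More than 2 dose-level reductions | off study | not listed as such; item 3 covers intolerable toxicity |

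Whether separate holds add up is also open. The allowance sentence in 7.0 speaks of a total, but the removal sentence does not.

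**2. What remains for a patient removed under 7.0.** Section 5.6 lists severe adverse events, disease-free survival and overall survival. Table 3 places the post-radiation assessment 6–12 weeks after radiation, for patients who continue past the interval assessment. No section schedules a response assessment for a patient taken off study for a hold or for dose reductions. That the visit is missed is therefore an inference; no sentence states it.

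**3. How such a patient is counted.** The schema text keeps the patient in the response evaluation. Section 10.1 requires examination and endoscopy findings before a response can be recorded, which points to non-responder. Section 10.3 does not say so for this group.

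**4. The plan's own precision figure.** The one-sided exact (Clopper-Pearson) 95% lower limit for x responders among n is the 5% quantile of Beta(x, n − x + 1). The inputs from 10.3 are n = 40 and a 30% rate, so x = 12. The result is 18.3%, a width of 11.7 points. Section 10.3 prints 16.6% and 13.4 points, so its figures are not reproduced at n = 40. With n = 30 and x = 9 the formula gives 16.6% and 13.4 points. At a 50% rate with n = 30 (x = 15) the width is 16.1 points, which also matches the printed maximum. This mismatch is a separate matter; both sample sizes are carried below.

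**5. Effect of losing responders.** Start from a 30% response rate and count each lost responder as a non-responder. The numbers lost (1 to 3) are an assumed range.

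| Responders lost | N=40 | Lower limit | Drop (points) | N=30 | Lower limit | Drop (points) |
|---|---|---|---|---|---|---|
| 0 | 12/40 | 18.3% | – | 9/30 | 16.6% | – |
| 1 | 11/40 | 16.3% | 2.1 | 8/30 | 14.0% | 2.6 |
| 2 | 10/40 | 14.2% | 4.1 | 7/30 | 11.5% | 5.1 |
| 3 | 9/40 | 12.3% | 6.0 | 6/30 | 9.1% | 7.5 |

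Drops are taken before rounding (18.31 − 16.25 = 2.06 for the first row at N=40). Each loss lowers the point estimate by 1/40 = 2.5 points or 1/30 = 3.3 points.

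**The case against.** Several points on the other side stand.

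- **Terminology.** Section 5.6 uses treatment and study loosely, so it and 7.0 could be read as one rule. The firm difference is may against will. Stopping treatment under 5.6 does not expressly secure the post-radiation assessment either. This narrows the contradiction, but it is also a reason to write one clear rule.
- **Treatment failure.** Section 2.1 asks about response to chemotherapy plus radiation. A patient who cannot tolerate the regimen and is never irradiated has no post-radiation response, and counting that patient as a non-responder is legitimate. The concern therefore covers only patients who are still irradiated after stopping chemotherapy and who respond.
- **Mitigation.** Section 7.0 lets patients with grade 2 or greater neuropathy drop oxaliplatin after at least 6 cycles and continue 5-fluorouracil. It also allows growth factor support. Both keep some patients from reaching either removal rule.
- **Early stops.** Table 3 starts after the interval assessment, so it offers no schedule to a patient who stops before then.

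A reader might go further and infer that 7.0 is bound to cost responders, that these patients drop out of the denominator, or that the trial's conclusion would change. The documents support none of these. They give no rate of holds or dose reductions. The schema text includes all patients in the response evaluation. Section 10.3 names no value that the lower limit must exceed.

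**Conclusion.** The point holds in a limited form. Following 7.0 leaves a patient who was responding at the interval assessment, and who later meets the hold or dose-reduction rule, with no scheduled post-radiation assessment, and 10.3 does not say how that patient counts. The result is avoidable missing data on the primary endpoint. The bias is downward, and it arises only for those who are still irradiated and respond.

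The size rests on assumed counts: about 2 points off the lower limit per lost responder at N=40, and about 2.6 at N=30, starting from the anticipated 30% rate and treating an unassessed patient as a non-responder. The true number may be zero. This should be corrected, with medium confidence, but it does not invalidate the design.

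**What to change.** **Sections 7.0 and 5.6 item 7.** State one rule: a hold beyond 28 days (saying whether cumulative or continuous), or a need for more than 2 dose-level reductions, ends mFOLFOX but not study participation. Patients past the interval assessment keep the Table 3 restaging assessment and, if irradiated, the post-radiation assessment. Table 3 times these visits from the last chemotherapy and from radiation, so this group needs no new visits. Patients who stop before the interval assessment are treated at the investigator's discretion and followed as in 5.6.

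**Section 10.3.** State that every patient who starts mFOLFOX is in the primary denominator and counts as a non-responder if there is no post-radiation assessment, whatever the reason.

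**Cost.** A short amendment to three sections. A few patients off chemotherapy keep assessments that are already scheduled. The non-responder rule is conservative: it will understate the rate if a true responder is still missed.

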8.0 Study Treatment Toxicities

8.1 Oxaliplatin

Common Toxicities:

- Peripheral neuropathy (may be dose limiting)
- Nausea
- Vomiting
- Diarrhea
- Fatigue
- Abdominal pain
- Constipation
- Increased liver transaminases AST and ALT
- Anemia
- Thrombocytopenia

Less Common Toxicities:

- Leukopenia
- Anorexia
- Cough

- Back or myalgias (muscle aches)
- Arthralgias (joint aches)
- Edema
- Flushing
- Skin Rash
- Alopecia
- Dyspepsia
- Dysgeusia
- Hypersensitivity
- Local site reaction with redness or swelling
- Increase serum creatinine

Rare but serious:

- Anaphylaxis
- Chest pain
- Shortness of breath
- Palmar-plantar erythrodysesthesia (hand-foot syndrome, with redness and/or pain)
- Sepsis
- Death

8.2 Leucovorin

Toxicities:

- Thrombocytopenia
- Pruritus
- Hypersensitivity
- Urticaria
- Wheezing
- Skin rash
- Erythema (redness)
- Toxicities of 5-fluorouracil are enhanced

Rare but Serious:

- Anaphylaxis
- Seizures
- Death

8.3 5-Fluorouracil

Common Toxicities:

- Anemia
- Thrombocytopenia

- Leukopenia
- Nausea
- Vomiting
- Anorexia
- Diarrhea
- Nail changes, brittle nails

Less Common Toxicities

- Chest pain
- Alopecia
- Headache
- Palmar-plantar erythrodysesthesia (hand-foot syndrome, with redness, pain)
- Venous hyperpigmentation
- Dermatitis

Rare but Serious:

- Vasospasm
- Myocardial Infarction
- Death

8.4 Short Course Radiation

Common Toxicities:

- Fatigue
- Diarrhea
- Rectal pain/pressure
- Perineal Skin irritation
- Dysuria

Less Common Toxicities

- Change in bowel habit
- Vomiting
- Abdominal Pain

Rare but Serious:

- Bowel Obstruction
- Fecal Incontinence
- Secondary Malignancy

9.0 Adverse Events Monitoring and Reporting

9.1 Definition of Adverse Event (AE)

Adverse events (AE) will be defined as any sign, symptom, illness, abnormal or adverse laboratory value, or experience that was not present at the start of treatment and occurs or worsens during the course of the therapy proposed regardless if related to that therapy.

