To our knowledge, there are no studies currently evaluating a complete response to full, upfront neoadjuvant chemotherapy with mFOLFOX plus short course CT in locally advanced rectal adenocarcinoma followed by surveillance. From review of available literature, we conclude that there is the potential for an identifiable population of patients that may benefit from treatment with systemic therapy and short course RT with a complete or near complete response, while sparing these patients the toxicity of a total mesorectal excision. Earlier phase II studies demonstrate a range of complete response from 25% to 65% for total neoadjuvant therapy, but we conclude from these studies that the complete response rate is likely in the range of 30-40%.

In conclusion, we hypothesize that some patients with locally advanced rectal cancer with stage I (T2N)-IIIB disease (excluding clinical T4 or N2b staging) will benefit from our proposed protocol of total neoadjuvant therapy, with proposed reduction in surgical related toxicities.

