3.0 Study Design

This is a multi-center, phase II study investigating the efficacy of total neoadjuvant therapy with mFOLFOX and short course radiation and selective non-operative management in patients with locally advanced rectal cancer.

Participants with Stage IIA, IIIA, IIIB rectal adenocarcinomas, except for any T4 or N2b disease, who would otherwise undergo long course concurrent chemotherapy and radiation therapy followed by TME may be enrolled for treatment with mFOLFOX therapy. Participants with lower sphincter rectal cancer deemed not eligible for sphincter sparing surgery are not eligible for participation. Participants would be treated with up to 12 cycles of mFOLFOX therapy. (One cycle of mFOLFOX= 14 days) and short course radiation.

All patients will be evaluated once following six cycles of chemotherapy via endoscopy and CT plus MRI.

Patients with a partial, near or complete response will receive an additional 4-6 cycles of chemotherapy followed by reassessment.

Patients with stable or progressive disease defined as less than 20% reduction will be removed from study.

Following completion of all chemotherapy (10-12 cycles) patients will be re-assessed via endoscopy and CT plus MRI. Patients will then receive short course radiation followed by repeat assessment with endoscopy and CT/MRI. Those patients with evidence of complete or near complete clinical response following completion of all chemotherapy and radiation will be treated non-operatively and undergo close surveillance.

Patients with a partial response or stable disease will undergo TME.

Those with <20% response will be removed from study and undergo treatment per the treating investigator. These patients will be followed for survival at six month intervals for up to 5 years.

All patients will be followed for 5 years following last date of treatment:

- For patients in the study not requiring surgery following chemotherapy, the last day of treatment will be considered the last day of mFOLFOX therapy.
- For patients who receive short course radiation, the last day of treatment will be considered the last day of radiation.
- For patients in the TME group, the last day of treatment will be considered the day of surgery.

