5.5 Post-treatment Evaluation

All patients will be subject to surveillance for 5 years to monitor for progression of disease. Patients on watch and wait surveillance will undergo history and physical examination, imaging, laboratory testing, and surgical oncology evaluation as outlined in Table 4. Those patients who received surgery after partial response will be followed per NCCN guidelines regarding history and physical exam, CEA, imaging, and evaluation by colonoscopy.

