^bLaboratory work can be obtained up to 48 hours prior to any treatment or assessment

Table 4. Surveillance following completion of total neoadjuvant therapy without surgery

	Year 1		Year 2		Year 3		Year 4		Year 5	
Months from completion of study	3-6	9-12	15-18	21-24	30	36	42	48	54	60
History/Physical Exam										
H&P	X	X	X	X	X	X	X	X	X	X
Performance Status	X	X	X	X	X	X	X	X	X	X
QOL ^a	X	X	X	X	X		X	X		X
Imaging										
MRI pelvis	X	X		X		X		X		X
CT chest/abdomen/pelvis	X	X		X		X		X		X
Procedural										
Proctoscopy or Sigmoidoscopy, and DRE	X	X	X	X	X	X	X	X	X	X
Laboratory										
CBC	X	X	X	X	X	X	X	X	X	X
CMP	X	X	X	X	X	X	X	X	X	X
CEA	X	X	X	X	X	X	X	X	X	X

^aQOL will be assess on all patients, including those that did not continue watch and wait surveillance as the proceeded to surgery

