11.0 Data and Safety Monitoring

11.1 Assessments and documentation of adverse events:

Adverse events and grade will be recorded at each follow-up visit. Serious adverse events will be collected and reported from the time patient signs informed consent until the first surveillance safety follow-up visit. Non-serious adverse events will be collected from the time of first study drug dosing until the first surveillance safety follow-up visit.

11.2 Reporting of serious adverse events:

The definition of serious adverse events (SAEs) is given in Section 9.2.

Each serious adverse event must be followed up until resolution or stabilization, by submission of updated reports to the designated person. An isolated laboratory abnormality that is assigned grade 4, according to CTC definition, is not reportable as an SAE; unless the investigator assesses that the event meets standard ICH criteria for an SAE. CTC grade 4 baseline laboratory abnormalities that are part of the disease profile should not be reported as an SAE, specifically when they are allowed or not excluded by the protocol inclusion/exclusion criteria.

When required, and according to local law and regulations, serious adverse events must be reported to the Ethics Committee and Regulatory Authorities.

Study Investigators will conduct continuous review of data and patient safety. The Investigator will submit twice yearly progress reports of these data to the Data Safety Monitoring Committee for review. The review will include: the number of patients enrolled, withdrawals, significant toxicities as described in the protocol, serious adverse events both expected and unexpected, dose adjustments, and responses observed. The PI maintains a database of all adverse events with toxicity grade and information regarding treatment required, complications, or sequelae. The Investigator will submit a copy of the AE spreadsheet along with a Progress Report to the Data Safety Monitoring Committee (DSMC) for review. Actual review dates will be assigned when the 1st patient is accrued.

The DSMC at the Wilmot Cancer Institute, University of Rochester provides oversight of study progress and safety by review of accrual and adverse events at twice yearly meetings or more often if concerns arise. Any adverse event requiring expedited review per protocol, including those occurring at participating sites, will be submitted to the Safety Coordinator of the DSMC at the University of Rochester for

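### Capture of complications after protocol or salvage TME is not assured by the adverse event definitions, the collection window or the visit tables

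*Combined protocol and SAP*

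**What the plan says.** **Definition.** Section 9.1 counts an event if it "occurs or worsens during the course of the therapy proposed regardless if related to that therapy". Section 9.2 carries the same time limit into the definition of a serious adverse event.

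**Place of surgery in the design.** Section 3.0 makes TME a step after chemotherapy and radiation: "Patients with a partial response or stable disease will undergo TME". It also fixes when treatment ends for these patients: "For patients in the TME group, the last day of treatment will be considered the day of surgery".

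**Collection window.** Section 11.1 states: "Serious adverse events will be collected and reported from the time patient signs informed consent until the first surveillance safety follow-up visit". For the rest: "Non-serious adverse events will be collected from the time of first study drug dosing until the first surveillance safety follow-up visit". The same section opens by asking that events and grades be recorded at every follow-up visit.

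**Schedule.** The row for reviewing medications and adverse events appears in Tables 2 and 3 only, and the last column of Table 3 is the post-radiation assessment. Table 4 is titled "Surveillance following completion of total neoadjuvant therapy without surgery" and has no such row. For operated patients Section 5.5 says: "Those patients who received surgery after partial response will be followed per NCCN guidelines". It names history and examination, CEA, imaging and colonoscopy.

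**Objectives and analysis.** Section 2.2 lists safety and toxicity as a secondary objective. Its only surgical outcome is the R0 resection rate. Section 10.3 tabulates types and grades of adverse events and has no item for surgical complications.

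**The concern.** The strategy avoids or defers surgery, and Section 1.2 justifies it by surgical morbidity, including wound dehiscence after chemoradiation, and by a hypothesised benefit "with proposed reduction in surgical related toxicities". The schema includes all patients in the evaluation of safety. Yet the text does not make clear that a leak, dehiscence, reoperation or readmission some days after TME is an event to be collected, or at which visit it would be asked about.

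Two outputs depend on this. One is the adverse event table of Section 10.3, which could show chemotherapy and radiation toxicity and little of what happened to operated patients. The other is reporting to the monitoring committee. Its review trigger (two or more of the same serious event in a month, or more than six in six months) can count only events that reach the database.

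**Working it through.** The plan gives no figure for surgical complications, so there is none to reproduce. The check is a reading of the rules in time order, followed by a count of the patients concerned.

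**Protocol TME**

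1. Last scheduled adverse event review: the post-radiation assessment, 6 to 12 weeks after radiation (Table 3). The decision for TME rests on that assessment, so the operation comes after the last scheduled review.
2. End of treatment: the day of surgery (Section 3.0). If the therapy in Section 9.1 includes TME, events on that day are covered. Later post-operative days are ambiguous.
3. End of collection: the first safety visit of surveillance (Section 11.1). No table has a visit of that name, and operated patients have no table. If their first guideline visit is meant, the weeks after surgery are inside the window. If a Table 4 visit is meant, it does not apply to them. The text does not say which.

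**Salvage TME**

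1. The first Table 4 visit is at 3 to 6 months. If that is the visit in Section 11.1, collection stops there.
2. Salvage surgery for regrowth found at that visit or later takes place after collection has stopped. In the cited watch-and-wait study (Section 1.2), 17 of 28 recurrences came within the first year, so 28 − 17 = 11 came later.
3. Table 4 has no adverse event row at any visit.

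**Number of patients concerned**

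Inputs: 30% response and N = 40 (Section 10.3); N = 30 (schema); 28 of 90 recurrences after complete clinical response, and salvage surgery feasible in 26 of those 28 (Section 1.2). Both sample sizes are shown because the document states both.

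| | N = 40 | N = 30 |
|---|---|---|
| Responders, 0.30 × N | 12 | 9 |
| Non-responders, N − responders | 28 | 21 |
| Recurrences, responders × 28/90 | 3.7 | 2.8 |
| Salvage operations, responders × 26/90 | 3.5 | 2.6 |

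The last row uses 28/90 × 26/28 = 26/90.

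The non-responder row is an upper bound on TME for non-response. Patients with stable or progressive disease at the interval assessment leave the study and are treated at the investigator's discretion. The bound cannot be tightened from the text. After radiation, Section 3.0 sends stable disease to TME and also removes patients with less than 20% response, which is how Section 10.1 defines stable disease. Those passages must be reconciled.

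**The case against.** The strongest reply is that the plan has several routes by which a surgical complication could be recorded.

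- Section 9.3 asks about events at every visit and lets an intervention be named as the suspected cause. Section 9.1 does not require relatedness.
- Section 9.2 counts hospitalisation, prolonged hospitalisation and death as serious outcomes.
- Section 11.1 asks for recording at each follow-up visit, and the principal investigator keeps a database of all events with complications and sequelae.
- Section 5.6 continues follow-up for severe events after discharge from treatment and study.
- Post-operative deaths count in overall survival, and quality of life is collected in operated patients.

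This stands in part. A reader might infer from Sections 9.1 and 3.0 together that post-operative events are excluded by definition. The documents do not support that, because Table 3 schedules adverse event review 4 to 12 weeks after the last chemotherapy and again 6 to 12 weeks after radiation. The plan therefore does not treat the course of therapy as ending with the last dose or fraction. Nor is it right that surgical complications could not be reported at all.

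The routes still do not close the gap. The request in Section 11.1 for recording at each follow-up visit is limited by the stopping point in its next two sentences. Section 5.6 concerns patients discharged from treatment and study, speaks of severe rather than serious events, and applies only where follow-up is possible. Survival and quality of life do not record a leak, a reoperation or a stoma. None of these clauses sets a post-operative period or a scheduled review.

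**Conclusion.** The point holds as a gap in assured capture. For protocol TME, recording depends on how an undefined visit is read. For salvage TME after that visit, complications fall outside routine collection. No post-operative window, scheduled review or summary is specified, so the safety tables and the committee's reports may miss these events. The primary endpoint, assessed after radiation, is not affected.

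The numbers are illustrative: about 3.5 of 12 responders at N = 40, or 2.6 of 9 at N = 30, with salvage surgery, and at most 28 of 40 or 21 of 30 with TME for non-response. They assume the plan's 30% response. They also assume that rates from a chemoradiation study of complete responders, followed for a median of 60 months, carry over to this regimen, where near complete responders are also put on surveillance. The 28 and 21 should not be read as expected numbers of operations.

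A reader might also infer that the gap prevents the trial from testing the hypothesised reduction in surgical toxicity. It would not do so with complete data either. That reduction is a statement of rationale, not an objective, and the trial has one arm with no comparator and no stated historical benchmark. Full capture would only describe complications.

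**What to change.** Reconcile Sections 9.1, 9.2, 11.1, 5.6 and Table 4 as follows:

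- State whether the therapy in Sections 9.1 and 9.2 includes TME, and extend collection of serious and non-serious events to a fixed period (for example 90 days) after any protocol or salvage TME.
- In Section 11.1, name the visit that ends routine collection for operated and for non-operated patients, and say that a later salvage TME reopens it for the fixed period.
- Abstract from the chart the CTCAE grade, reoperation, readmission, stoma and death.
- State whether TME after removal from the study is included. Section 2.2 already takes the R0 rate from patients operated on after stable or progressive disease.
- In Section 10.3, tabulate these events descriptively and separately for initial and salvage TME, with the number operated on as denominator, and make no claim to estimate a reduction in surgical toxicity.

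The cost is protocol wording, one chart-abstraction form and some extra data entry. No visit or procedure is added, and the surgical records must be opened for the R0 rate in any case.
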